
Change from baseline in subject functional impairment domain score at week 24, as measured by the Migraine Functional Impact Questionnaire (MFIQ)
 
 – Physical function domain score – Usual activities domain score – Emotional function domain score – Social function domain score 	
1. Summary statistics using observed data (after intercurrent event handling);
 
2. The change from baseline in subject functional impairment domain score at week 24, as measured by the MFIQ will be analyzed using a generalized linear mixed effects model with the identity link function. The model will include baseline subject functional impairment domain score, visit, the prevailing erenumab dose from Week 12 onwards, and baseline MMD based on observed data. The mean change from baseline in subject functional impairment domain score at week 24 with the corresponding 95% CI will be estimated from the LSM of the mixed effects model, and p-values comparing with zero at a two-sided 5% significance level will be reported.

Endpoint	Primary Summary and Analysis Method
	
3. The efficacy analysis set will be used for this endpoint analysis.
 
4. This endpoint will be analyzed separately for each functional domain.

Table 9-3. Exploratory Efficacy Endpoint Summary Table

Endpoint	Primary Summary and Analysis Method
Change from baseline in TSQM overall satisfaction scale score at weeks 12, 16, and 20 and mean over weeks 16, 20, and 24	This endpoint will be analyzed same as primary efficacy endpoint.
Achievement of overall satisfaction as defined by subject reporting of satisfied, very satisfied, or extremely satisfied on item 14 of the TSQM version 1.4 at weeks 12, 16, and 20.	This endpoint will be analyzed same as primary efficacy endpoint.
Change from baseline in TSQM sub-scale domain scores at weeks 12, 16, 20 and 24 and mean over weeks 16, 20, and 24: – effectiveness – side effects – convenience	This endpoint will be analyzed same as primary efficacy endpoint. Note: Use baseline value covariate as a “Baseline TSQM sub-scale domain score”
Improvement in subject global impression at weeks 12, 16, and 20, as defined by subject reporting of much improved or a little improved on the mGI-I Improvement in treating clinician's global impression at weeks 12, 16, and 20, as defined by treating	This endpoint will be analyzed same as above mentioned mGI-I endpoint.

Endpoint	Primary Summary and Analysis Method

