
clinician's reporting of much improved or a little improved on the mGI-I
 
Improvement in key family member's global impression at weeks 12, 16, and 20, as defined by key family member's reporting of much improved or a little improved on the mGI-I
	

Change from baseline in MFIQ functional impairment domain scores, at weeks 12, 16, and 20, and mean over weeks 16, 20, and 24:
 
 – Impact on physical function – Impact on usual activities – Impact on emotional function – Impact on social function 	
 1. Summary statistics by visit using observed data at each visit, and the calculated mean MFIQ physical function impairment domain score over weeks 16, 20, and 24. 2. The change from baseline in physical function impairment domain score at weeks 12, 16, and 20, and mean over weeks 16, 20, and 24, as measured by the MFIQ will be analyzed using a generalized linear mixed effects model with the identity link function. The model will include baseline MFIQ physical function domain score, visit, the prevailing erenumab dose from Week 12 onwards, and baseline MMD based on observed data. The mean change from baseline in physical function impairment domain score at weeks 12, 16, and 20, and mean over weeks 16, 20, and 24 with the corresponding 95% CI will be estimated from the LSM of the mixed effects model. 3. The efficacy analysis set will be used for this endpoint analysis.

Endpoint	Primary Summary and Analysis Method
Achievement of at least a 50% reduction from baseline in mean MMD over weeks 16, 20, and 24	
 1. Summary statistics by visit using observed data at each visit, and at least a 50% reduction from baseline in mean MMD over weeks 16, 20, and 24. 2. The achievement of at least a 50% reduction from baseline in mean MMD over weeks 16, 20, and 24 will be analyzed using a generalized linear mixed effects model with the logit link function. The model will include the prevailing erenumab dose from Week 12 onwards, and baseline MMD. The probabilities and the corresponding 95% CI for 50% reduction from baseline MMD in mean MMD over months 4 to 6 will be estimated using the mixed effects model. 3. The efficacy analysis set will be used for this endpoint analysis.

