Achievement of at least a 50% reduction from baseline in MMD at weeks 16, 20, and 24	
 ○ Summary statistics by visit using observed data at each visit, and at least a 50% reduction from baseline in MMD at weeks 16, 20, and 24. ○ The change from Achievement of at least a 50% reduction from baseline in MMD at weeks 16, 20, and 24 will be analyzed using a generalized linear mixed effects model with the logit link function. The model will include achievement of at least a 50% reduction from baseline in MMD, visit, the prevailing erenumab dose from Week 12 onwards, and baseline MMD.

Endpoint	Primary Summary and Analysis Method
	
The probabilities and the corresponding 95% CI for at least 50% reduction from baseline MMD at weeks 16, 20, and 24 will be estimated using the mixed effects model.
 
 ○ The efficacy analysis set will be used for this endpoint analysis.

The same analysis methods will be applied to the below exploratory endpoints:

Change from baseline in the Migraine Symptom Severity Scale (MSSS) total score at weeks 12, 16, 20, and 24 and mean over weeks 16, 20, and 24

Change from baseline in the Migraine Interictal Burden Scale (MIBS-4) total score at weeks 12, 16, 20, and 24 and mean over weeks 16, 20, and 24

Change from baseline in mean MMD over weeks 16, 20, and 24

Change from baseline in MMD at weeks 16, 20, and 24

Change from baseline in mean monthly acute migraine-specific medication days over weeks 16, 20, and 24

Change from baseline in monthly acute migraine-specific medication days at weeks 16, 20, and 24

Change from baseline in General Anxiety Disorder scale (GAD-7) total score at weeks 12 and 24

Change from baseline in Patient Health Questionnaire (PHQ-9) total score at weeks 12 and 24

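### Two exploratory rows of SAP Table 9-3 name the wrong model: the 50% MMD response is a covariate for itself, and yes/no Item 14 satisfaction at weeks 12 to 20 follows the continuous primary analysis

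*SAP*

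**What the plan says.** Both rows are in Table 9-3 (SAP Section 9.5). Protocol Section 9.4.2.2 leaves exploratory methods to the SAP, so this table is the governing text.

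**Row 1, 50% MMD response at weeks 16, 20 and 24.** The link is logit. The outcome is introduced with "The change from Achievement of at least a 50% reduction from baseline in MMD at weeks 16, 20, and 24 will be analyzed", the covariates with "The model will include achievement of at least a 50% reduction from baseline in MMD, visit, the prevailing erenumab dose from Week 12 onwards", followed by baseline MMD. The promised output is "The probabilities and the corresponding 95% CI for at least 50% reduction from baseline MMD at weeks 16, 20, and 24 will be estimated". The neighbouring row, for a 50% reduction in mean MMD over the three months, has no such term: "The model will include the prevailing erenumab dose from Week 12 onwards, and baseline MMD".

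**Row 2, Item 14 at weeks 12, 16 and 20.** The endpoint is a yes/no classification: satisfied, "very satisfied, or extremely satisfied on item 14 of the TSQM version 1.4 at weeks 12, 16, and 20". The whole method is one sentence: "This endpoint will be analyzed same as primary efficacy endpoint". The primary (Table 9-1 and Section 9.5.1) is a repeated measures mixed model of change in the overall satisfaction scale score. It is adjusted for that score at baseline and reports a least-squares mean change with a nominal p-value against zero. Section 8.6 assumes normality for change-from-baseline endpoints. For the same item at week 24, Table 9-2 and Section 9.5.2 specify a logit mixed model with baseline achievement of satisfaction as the covariate, reporting a proportion.

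**The concern.** An outcome cannot be a covariate in its own regression. A programmer who follows row 1 to the letter gets a fit that does not converge, and the probabilities and intervals that the row promises cannot be produced from it.

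Row 2 is less conspicuous. A linear mixed model fitted to 0/1 data runs without complaint, so the mismatch could pass into the tables unnoticed. One item would then be reported from two models, with different links and different baseline covariates, at weeks 12 to 20 and at week 24. A reader who sees the four values as one time course could not separate a change in satisfaction from a change of method.

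What is at stake is whether the plan can be executed and whether the visits are consistent with each other, in exploratory output only.

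**Working it through.** The plan states no figure for these rows, so there is none to reproduce. The check is of the model specifications.

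**Row 1, literal reading.** Let y be the 0/1 response, and let c be the coefficient of y when y is also a covariate. Take the linear predictor as −c/2 + c·y, with all other effects zero. Every observation then contributes −ln(1 + exp(−c/2)) to the log-likelihood. With the effective sample size of 216 in SAP Section 3.2 and three visits, complete data give 216 × 3 = 648 observations:

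| c | log-likelihood = −648 × ln(1 + exp(−c/2)) |
|---|---|
| 10 | −4.35 |
| 20 | −0.029 |
| 40 | −0.0000013 |

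The log-likelihood rises towards its upper bound of zero as c grows and never reaches it, so no finite maximum exists. This does not depend on any assumed response rate. A random-intercept logit fit to simulated data behaved the same way: the coefficient was 13.7, 33.2 and 79.4 after 10, 20 and 40 iterations, and the log-likelihood was −0.81, −0.006 and −0.000006.

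**Row 1, baseline reading.** In parallel rows the first covariate is the endpoint's baseline value. By the formula in SAP Section 5.5, percent change at baseline is (baseline − baseline) / baseline × 100 = 0. Inclusion criterion 108 requires at least 4 MMD, so the denominator is not zero. The response at baseline is therefore no for every subject. The design has an intercept, two visit terms, dose and baseline MMD (5 columns). The added column makes 6, and the rank stays 5. Fitted probabilities with and without it differed by less than 0.000001 in three simulated scenarios.

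**Row 1, term deleted.** In those scenarios (216 subjects; response of about 40%, 50% or 60% and random-intercept SD of 2, all assumed) the model with visit, dose and baseline MMD gave finite week 24 estimates with intervals: 38.0% (27.0 to 50.4), 57.1% (45.3 to 68.1) and 63.5% (52.6 to 73.1). The corrected row can be fitted.

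**Row 2, the two specifications for one item.**

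| | Weeks 12, 16, 20 (Table 9-3) | Week 24 (Table 9-2, Section 9.5.2) |
|---|---|---|
| Model | As the primary: continuous change score, normality | Logit mixed model |
| Baseline covariate | Overall satisfaction scale score | Achievement of satisfaction (yes/no) |
| Reported quantity | Least-squares mean, p-value against zero | Proportion by inverse link |
| Intercurrent-event handling | None (Sections 9.1, 9.5.3) | Yes |

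The rows around it show that the table adapts methods where needed. The sub-scale row replaces the baseline covariate ("Note: Use baseline value covariate as a" sub-scale score), and the global impression row refers to its own logit model ("This endpoint will be analyzed same as above mentioned mGI-I endpoint"). The Item 14 row does neither.

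**Other text that might correct the rows.** Section 9.5.3 says exploratory endpoints follow the primary and secondary methods, without saying which applies where, and refers to Table 9-3. Section 10, on changes from the protocol, mentions neither row.

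**The case against.** The strongest reply is that these are drafting slips with little practical effect, and much of it stands. Row 1 looks like a template slot for a baseline value that was filled with the wrong phrase. Read as a baseline value it does no harm, and read literally it would fail visibly at the first run and could not produce a misleading number. For row 2, Section 9.1 calls for counts and percentages of categorical endpoints at each timepoint of interest, and the primary method begins with summary statistics. Observed Item 14 percentages at weeks 12, 16 and 20 are therefore planned whichever model is used. Section 9.5.3 also gives a programmer some cover for choosing the secondary logit model. It does not cure the row's explicit instruction, because the row names the primary method and Section 9.5.3 defers to the table.

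Three stronger readings should be resisted.

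- A reader might infer that the linear estimate is biased. With a flat true rate of 70%, the logit inverse-link estimate at a random effect of zero is 70.0%, 73.5% or 80.0% for an assumed random-intercept SD of 0, 1 or 2, a gap of 0 to 10 points. The linear model returns the observed 70%; it is the logit estimate that departs from it. The SAP does not give the random-effect structure, so this shows that the two models need not agree, not that the linear one is wrong.
- A reader might infer that row 2 will report a change in proportion. The row does not say that the change score is carried over, and the documents give no baseline satisfied rate.
- A reader might try to size the effect of intercurrent-event handling on the week 24 figure. That needs the share of subjects stopping for lack of efficacy or adverse event, and their satisfaction otherwise. The documents give neither; the 10% in Section 3.2 is total dropout.

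**Conclusion.** Both rows are wrong as written. Row 1 cannot be fitted if taken literally and carries a redundant term if taken as a baseline value; neither reading is a reason to keep the term. Row 2 assigns a binary endpoint to a method for a continuous change score, with a baseline covariate that differs from the one used for the same item at week 24.

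The consequence is low. The study is descriptive, both endpoints are exploratory, no primary or secondary result changes, and observed by-visit percentages for both endpoints are reported regardless. The case rests on having a model that can be run and a consistent model across visits.

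The row 1 conclusion needs no numerical assumption. The row 2 conclusion rests on reading the primary model as linear. The SAP does not use that word, but the change-score outcome, the normality statement and the test of a mean against zero support it.

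**What to change.** **Row 1.** Delete the 50% response from the covariate list and keep visit, prevailing erenumab dose and baseline MMD. Also delete the words about change that precede the outcome.

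**Row 2.** Refer the row to the secondary Item 14 model in Table 9-2: logit link, with baseline achievement, visit, dose and baseline MMD. State that it is fitted without intercurrent-event handling, as Sections 9.1 and 9.5.3 require for exploratory endpoints.

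The row 2 fit is separate from the secondary week 24 fit, which does use intercurrent-event handling, so a single fit cannot supply both sets of results as specified. The exploratory fit can include week 24 without handling. Either show that value beside weeks 12, 16 and 20, or add a footnote saying that the secondary week 24 value is handled differently.

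The cost is two text edits in Table 9-3 and either one extra week 24 estimate or a footnote. Row 2 needs its own exploratory model fit. No new data are needed, and the primary and secondary analyses stay as they are.

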9.5.1 Analyses of Primary Efficacy Endpoint(s)/Estimand(s)

The primary endpoint, the change from baseline in the TSQM overall satisfaction scale score at week 24, as measured by items 12 to 14 of the TSQM version 1.4 will be analyzed using a repeated measures mixed effects model, including baseline TSQM overall satisfaction scale score, visit, the prevailing erenumab dose from Week 12 onwards, and baseline MMD **based on observed data**.

The mean change from baseline in TSQM overall satisfaction scale score at week 24 will be estimated from the least-squares mean (LSM) of the mixed effects model, and the corresponding 95% CI will be provided. The nominal p-value will be reported by comparing the mean change from baseline in TSQM overall satisfaction scale score at week 24 to zero with a two-sided 5% significance level.

This endpoint will be analyzed using the following subgroups **respectively**:

- Whether remained on standard of care migraine preventive throughout the study (yes vs. no)
- Migraine type (EM vs. CM)

The subgroups will be re-examined for appropriateness and may be re-categorized (due to small sample size, for example, if there are < 10% of subjects within a subgroup) before final analysis.

The purpose of the subgroup analyses is to explore if the treatment effect varies across subgroups of interest. Subgroup analyses will be performed using the same method as primary analysis method but within level of each subgroup of interest.

The efficacy analysis set will be used for this endpoint analysis.

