9.4.2.2 Efficacy Analyses

Endpoint/ Estimand	Statistical Analysis Methods
Primary	
In the event of IP discontinuation due to lack of efficacy or adverse event, the TSQM overall satisfaction scale score after treatment discontinuation will be defined as the worst postbaseline value observed up to IP discontinuation (inclusive). Any TSQM data collected after treatment discontinuation due to other reasons will be censored and not included in the analysis.
 
The primary endpoint will be analyzed using a repeated measures mixed effects model, including baseline TSQM overall satisfaction scale score, visit, the prevailing erenumab dose from week 12 onwards, and baseline MMD based on observed data. The mean change from baseline in TSQM overall satisfaction scale score at week 24 will be estimated from the least-squares mean (LSM) of the mixed effects model, and the corresponding 95% CI will be provided. The nominal p-value will be reported by comparing the mean change from baseline in TSQM overall satisfaction scale score at week 24 to zero with a two-sided 5% significance level.

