2.1 Objectives and Endpoints/Estimands

Objectives	Endpoints
Primary	

 To evaluate the effect of erenumab on medication-specific treatment satisfaction 	
 Change from baseline in the Treatment Satisfaction Questionnaire for Medication (TSQM) overall satisfaction scale score at week 24, as measured by items 12 to 14 of the TSQM version 1.4
Primary Estimand	

The estimand for the primary efficacy objective consists of:
 
 The target population, which includes subjects with Episodic Migraine (EM) or Chronic Migraine (CM) currently on 1 standard of care migraine prevention therapy The endpoint, which is the change from baseline in TSQM overall satisfaction scale score at week 24, as measured by items 12 to 14 of the TSQM There are 2 intercurrent events, discontinuation of investigational product (IP) due to lack of efficacy or adverse event, and discontinuation of IP due to other reasons. The treatment effect of interest will be assessed for all subjects who receive least 1 dose of IP and have a baseline score and at least 1 post-baseline score on the TSQM overall satisfaction scale. A composite strategy will be used for subjects who discontinued IP due to lack of efficacy or adverse event with data after IP discontinuation, defined by the worst postbaseline 	

value observed up to IP discontinuation (inclusive). A hypothetical strategy will be used for those subjects who discontinued IP due to other reasons with data collected after IP discontinuation censored.

- The treatment, which is erenumab 70 or 140 mg every 4 weeks
- The summary measure, which is the mean change from baseline in TSQM overall satisfaction scale score at week 24, as measured by items 12 to 14 of the TSQM

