The primary estimand for the primary efficacy objective is the mean change from baseline in TSQM overall satisfaction scale score at week 24 in subjects with EM or CM who are currently on 1 standard of care migraine prevention therapy and who receive at least 1 dose of IP and have a baseline and at least 1 post-baseline TSQM overall satisfaction scale score, and a composite strategy will be used for subjects who discontinued IP due to lack of efficacy or adverse event with data after IP discontinuation defined by the worst postbaseline value observed up to IP discontinuation (inclusive), while a hypothetical strategy will be used for those subjects who discontinued IP due to other reasons with data collected after IP discontinuation censored.

Secondary

• To assess the effect of erenumab on medication-specific treatment satisfaction	
• Achievement of overall satisfaction at week 24 as defined by subject reporting of satisfied, very satisfied, or extremely satisfied on Item 14 of the TSQM version 1.4
--	--

The estimand for the secondary efficacy objective on treatment satisfaction consists of:

- The target population, which includes subjects with EM or CM currently on 1 standard of care migraine prevention therapy
- The endpoint, which is achievement of overall satisfaction at week 24 as defined by subject reporting of satisfied, very satisfied, or extremely satisfied on Item 14 of the TSQM

- There are 2 intercurrent events, discontinuation of IP due to lack of efficacy or adverse event, and discontinuation of IP due to other reasons. The treatment effect of interest will be assessed for all subjects who receive at least 1 dose of IP and have a baseline value and at least 1 post-baseline value for Item 14 of the TSQM. A composite strategy will be used for subjects who discontinued IP due to lack of efficacy or adverse event where they will be defined as not satisfied after IP discontinuation. A hypothetical strategy will be used for those subjects who discontinued IP due to other reasons with data collected after IP discontinuation censored.
- The treatment, which is erenumab 70 or 140 mg every 4 weeks
- The summary measure, which is the proportion of subjects who achieves overall satisfaction at week 24

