9.5.2 Analyses of Secondary Efficacy Endpoint(s)

The secondary efficacy endpoints calculated by the methods as specified detailed in [Table 9-2](#). Secondary Efficacy Endpoint Summary Table, column Primary Summary and Analysis Method.

For continuous secondary endpoints, a generalized linear mixed effects model with the identity link function will be used. The model will include the corresponding baseline value for the endpoint being analyzed, visit, the prevailing erenumab dose from Week 12 onwards, and baseline MMD. The corresponding 95% CI will be estimated from the LSM of the mixed effects model, and p-values comparing with zero at a two-sided 5% significance level will be reported.

For binary secondary endpoints, a generalized linear mixed effects model with the logit link function will be used. The model will include the corresponding baseline value for the endpoint being analyzed (except for the global impression endpoints), visit, the prevailing erenumab dose from Week 12 onwards, and baseline MMD. The proportions and the corresponding 95% CI will be estimated from the LSM (with inverse link function) of the mixed effects model and will be reported.

The secondary endpoints will be analyzed in the following subgroups:

- Whether remained on standard of care migraine preventive treatment throughout the study (yes vs. no)
- Migraine type (EM vs. CM)

The subgroups will be re-examined for appropriateness and may be re-categorized (due to small sample size, for example, if there are < 10% of subjects within a subgroup) before final analysis.

The purpose of the subgroup analyses is to explore if the treatment effect varies across subgroups of interest. Subgroup analyses will be performed using the same method as primary analysis method but within level of each subgroup of interest.

The efficacy analysis set will be used for this endpoints analyses.

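### The TSQM and MFIQ mean-change CIs omit covariate sampling error, so they are too narrow for the population estimand whenever baseline score, MMD or dose explains part of the change

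*SAP*

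**What the plan says.** **Estimand.** SAP 2.1 states that the primary estimand "is the mean change from baseline in TSQM overall satisfaction scale score at week 24 in subjects with EM or CM". The target population is described as "currently on 1 standard of care migraine prevention therapy". It is not restricted to, or conditioned on, any baseline score, migraine frequency or dose mix. The MFIQ estimands have the same form.

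**Estimator.** SAP 9.5.1 and Table 9-1 fit a repeated measures mixed model "including baseline TSQM overall satisfaction scale score, visit, the prevailing erenumab dose from Week 12 onwards, and baseline MMD". The week-24 mean change will "be estimated from the least-squares mean (LSM) of the mixed effects model, and the corresponding 95% CI will be provided". For the four MFIQ domains, SAP 9.5.2 says: "The corresponding 95% CI will be estimated from the LSM of the mixed effects model".

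**Test.** Protocol 9.4.2.2 says: "The nominal p-value will be reported by comparing the mean change from baseline in TSQM overall satisfaction scale score at week 24 to zero". SAP 9.5.1 repeats the comparison "to zero with a two-sided 5% significance level". MFIQ p-values against zero are planned in the same way, and the subgroup analyses reuse the method within each level.

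**What is not stated.** Neither document gives the covariate values at which the LS-mean is evaluated, how the two dose levels are weighted, or any variance other than the model's own. No bootstrap, robust or unadjusted CI is planned. The only primary sensitivity analysis (SAP 9.1) drops the intercurrent-event handling. Means, SDs and standard errors are planned as summary statistics, without a CI.

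**The concern.** An LS-mean standard error normally treats the covariate values at which it is evaluated as known constants. In a two-arm difference this does little harm, because sampling error in the covariate means cancels between arms. Here the reported quantity is one arm's mean, so nothing cancels.

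Change is the week-24 score minus the baseline score, so baseline will generally explain some of its variance. That share is left out of the standard error, although a new sample from the target population would have a different baseline average. The shortfall is proportional and does not shrink as n grows.

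The primary CI, the four MFIQ CIs, their nominal p-values and the subgroup fits are all affected. In a single-arm descriptive study, estimates with intervals are the main product. The report could also show a model standard error and a raw standard error for nearly the same mean, with no explanation of why they differ.

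**Working it through.** **1. The plan's own precision figures.** SAP 3.2 gives half-widths for proportions only. 1.96 × sqrt(p(1−p)/216) at p = 50, 60, 70 and 80% gives 6.67, 6.53, 6.11 and 5.33, against the stated 6.7, 6.5, 6.1 and 5.3. With 289 the results are 5.76, 5.65, 5.28 and 4.61, against 5.8, 5.6, 5.3 and 4.6. These figures reproduce and are not affected by this point. No precision figure is given for a continuous endpoint.

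**2. Inputs.** Effective n = 216 (SAP 3.2: 240 less 10%). The documents give no baseline SD (s0), week-24 SD (s1) or correlation between them (rho), so all three are assumed below.

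**3. Formulas, with baseline score as the covariate.**
- Var(change) = s0² + s1² − 2·rho·s0·s1
- Residual variance given baseline = s1²(1 − rho²)
- SE ratio (model ÷ true) = sqrt(residual variance ÷ Var(change)) = sqrt(1 − R²)
- Coverage = 2Φ(1.96 × SE ratio) − 1
- With equal SDs, R² = (1 − rho)/2

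| s1/s0 | rho | SE ratio | Coverage of nominal 95% CI | Correct width ÷ reported |
|---|---|---|---|---|
| 1 | 0 | 0.707 | 83.4% | 1.41 |
| 1 | 0.3 | 0.806 | 88.6% | 1.24 |
| 1 | 0.5 | 0.866 | 91.0% | 1.15 |
| 1 | 0.7 | 0.922 | 92.9% | 1.08 |
| 1 | 0.9 | 0.975 | 94.4% | 1.03 |
| 1.5 | 0 | 0.832 | 89.7% | 1.20 |
| 1.5 | 0.5 | 0.982 | 94.6% | 1.02 |

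Example for the last row: Var(change) = 1 + 2.25 − 1.5 = 1.75; residual = 2.25 × 0.75 = 1.6875; ratio = sqrt(1.6875/1.75) = 0.982.

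The true level of the nominal 5% test is one minus coverage: 16.6% at R² = 0.5, 9.0% at 0.25 and 5.6% at 0.05.

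**4. On the score scale** (assumed SD 20 at both times, n = 216). The half-width should be 3.58 rather than 2.65 points at rho 0.1, 2.67 rather than 2.31 at rho 0.5, and 1.19 rather than 1.16 at rho 0.9.

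**5. Simulation of the planned model.** Four visits, unstructured covariance, baseline score, dose and MMD as covariates, 240 subjects, 10% random dropout, SD 20, observed margins, 3000 runs per setting. At rho 0.1, 0.3, 0.5 and 0.7, coverage was 85.8%, 89.9%, 92.0% and 92.8%. The model SE was 0.75, 0.82, 0.89 and 0.93 times the empirical SE. Average estimates were 14.98 to 15.02 against a true 15, so this mechanism causes no bias.

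**6. Does the correction work?** In a week-24 check with dose and MMD in the model (n = 216, equal SDs), coverage was 84%, 87%, 91% and 92% at rho 0, 0.2, 0.5 and 0.7. Adding b'S(x)b/n to the LS-mean variance restored about 95%.

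**7. Dose weighting** (assumed 80/20 split, rho 0.3). Weighting the two doses equally, with no dose difference, gave 91.3% coverage. With an assumed 8-point dose difference, equal weighting gave an average estimate of 17.4 against a true 15 and 63% coverage. Observed margins gave 15.0 and 89.4%. Margins therefore need stating before any variance correction can do its job.

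**The case against.** The strongest case on the other side has five parts.

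- **The study is descriptive.** It has no hypothesis or comparator, the p-value is nominal, no success threshold is tied to TSQM or MFIQ means, and the sample size rests on proportions. This stands, and it limits the severity. It does not make a 95% label right for an interval that covers less.
- **The size is unknown.** This stands. Entry requires intolerance or insufficient response to the current preventive (Protocol 5.1, criterion 106), which may compress baseline TSQM scores and make the week-24 spread relatively larger. At s1/s0 = 1.5 and rho 0.5 the loss is negligible.
- **Low correlation is argued only for TSQM.** This stands. Protocol Table 1-1 has TSQM rate the standard of care drug on day 1 and only erenumab later, so a weak correlation is plausible. MFIQ measures migraine impact at both times, and the argument does not carry over.
- **A conditional CI is common practice and could simply be labelled as such.** Labelling would be honest, but it would leave the stated estimand without an interval of its own.
- **Raw standard errors are already planned.** If they are produced for change scores, a reader can build an unconditional interval. That is partial mitigation, but the SAP does not present it as such.

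A reader might also infer that the primary estimate itself is biased, given the equal-weighting result. The documents do not support that: they state no dose weighting, and the 8-point difference and 80/20 split are assumptions.

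**Conclusion.** The point holds as a should-fix. The target is a population mean change, but the planned interval and p-value carry only the variance conditional on the observed baseline score, MMD and dose mix. That is inferred from how an LS-mean standard error ordinarily works, because the SAP specifies no other variance.

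The interval is too narrow to the extent that those covariates explain the change. Under equal SDs, coverage runs from about 83% (rho 0) through 91% (rho 0.5) to 94% (rho 0.9). With a week-24 SD 1.5 times baseline it is about 90% (rho 0) and 95% (rho 0.5). The lower correlations are a reasoned possibility for TSQM only.

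A reader might go further and conclude that the CIs certainly cover well below 95%, or that the primary finding would be unreliable. The documents give no SD or correlation from which to show the first. As for the second, the standard-error issue leaves the point estimate alone and no formal decision depends on the p-value.

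**What to change.** In SAP 9.5.1, 9.5.2 and Tables 9-1 and 9-2:

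1. Keep the planned model. Protocol 9.3.1 calls for the baseline value and baseline MMD as covariates, so modelling baseline as a response instead would be a departure to record in SAP Section 10.
2. State that the LS-mean is evaluated at observed margins: sample means of baseline score and baseline MMD, and the observed dose distribution.
3. Obtain the 95% CI and p-value with an unconditional variance. Either bootstrap subjects, refitting the model and recomputing the margins in each resample, or add b'S(x)b/n to the LS-mean variance. Here b holds the week-24 coefficients of baseline score, MMD and dose, S(x) is the sample covariance matrix of those covariates, and n is the number of subjects over whom the margins are taken.
4. Do the same in the subgroup fits, with margins and n taken within each level.

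The cost is some SAP wording and a little programming, with no new data. The CI becomes wider, by up to about 1.4 times under the assumptions shown and by only a few percent if the covariates explain little of the change.
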